## 2.2 Secondary Objectives

- To describe the change in HAQ DI score at 12 weeks after the initiation of adalimumab, in those patients continuing on adalimumab (as observed population). This change will be summarized as the mean and 95% confidence interval or median (Q1,Q3) and will be tested with a paired t-test or a paired Wilcoxon signed-rank test without adjusting for baseline disease severity. For sensitivity analysis, the mean change in HAQ DI at Week 12 will be analyzed using ANCOVA adjusting for baseline disease severity.
- To describe the change in other patient reported outcomes (SF-36 domain scales, EQ-5D-3L index, WPAI total lost productivity) at weeks 12 and 24 after the initiation of adalimumab, in those patients continuing on adalimumab (as observed population). These changes will be summarized as the means and 95% confidence intervals or median (Q1,Q3) and will be tested with paired t-tests or paired Wilcoxon signed-rank tests.
- To summarize the number and percent of patients achieving a clinically meaningful improvement on the HAQ DI, as defined by a -0.22 point improvement or greater, at weeks 12 and 24 after the initiation of adalimumab, in those patients continuing on adalimumab (as observed population).

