#### **Questions**

Q1 = currently employed

Q2 = hours missed due to specified problem

Q3 = hours missed other reasons

Q4 = hours actually worked

Q5 = degree problem affected productivity while working

Q6 = degree problem affected regular activities

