#### **Scores**

Multiply scores by 100 to express in percentages.

- Percent work time missed due to problem  

$$Q2 / (Q2+Q4)$$

- Percent impairment while working due to problem  

$$Q5 / 10$$

- Percent overall work impairment due to problem

$$Q2/(Q2+Q4)+[(1-Q2/(Q2+Q4)) \times (Q5/10)]$$

- Percent activity impairment due to problem  

$$Q6 / 10$$

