## **4. SAMPLE SIZE AND POWER**

Approximately 100 patients diagnosed with RA will be recruited. The sample size was calculated by assuming an alpha of 0.05 and a power of 0.80 in a two-sided test, resulting in 52 subjects required to recognize a statistically significant improvement in HAQ DI (-0.21) (11). Given the importance of other secondary endpoints, an improvement of 9.9±25 hours of work time lost requires 58 subjects, assuming an alpha of 0.05 and a power of 0.80 in a two-sided test (12). However, since it is expected that approximately half the study population may no longer be working due to their age, approximately twice this number (100 patients) will be required to achieve the required number of respondents. We have also assumed a drop-out rate of 13% (assuming between 10%-15%).

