### 5.4 Analysis Plan for Secondary Objectives

In addition to HAQ DI score, the effect of adalimumab will also be assessed by the secondary outcome measures which are changes to the Short Form 36-Item Health Survey (SF-36) domain scores, EuroQol 5 dimension 3 level (EQ-5D-3L) index, WPAI outcomes, and Patient Treatment Satisfaction Questions at 12 and 24 weeks after the initiation of adalimumab in RA.

- As to the Short Form 36-Item Health Survey (SF-36) domain scores, the Excel Table 4 summarizes the changes in PCS T-score and MCS T-score at 12 and 24 weeks after the initiation of adalimumab; these changes will be summarized as the mean, SD, minimum, maximum, median, Q1, Q3; and the mean or median change will be tested with paired t-tests or paired Wilcoxon signed-rank test .
- As to the EuroQol 5 dimension 3 level quality of life questionnaire, the Excel Table 5 summarizes the changes in EQ-5D-3L index at 12 and 24 weeks after the initiation of adalimumab; these changes will be summarized as the mean, SD, minimum, maximum, median, Q1, Q3; and the mean or median change

will be tested with paired t-tests or paired Wilcoxon signed-rank test .

- As to the WPAI outcomes, the Excel Table 6 summarizes the changes in percent overall work impairment and percent activity impairment at 12 and 24 weeks after the initiation of adalimumab; these changes will be summarized as the mean, SD, minimum, maximum, median, Q1, Q3; and the mean or median change will be tested with paired t-tests or paired Wilcoxon signed-rank tests.

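### SAP Section 4 claims 80% power for hours of work time lost, but no planned analysis tests hours, so the figure describes none of the listed WPAI tests

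*SAP*

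**What the plan says.** SAP Section 4 gives two calculations. One is for HAQ DI. The other is justified by the importance of the secondary endpoints: "an improvement of 9.9±25 hours of work time lost requires 58 subjects, assuming an alpha of 0.05 and a power of 0.80", two-sided. The SAP then expects about half the patients not to be working, plans roughly twice as many (100), and assumes 13% dropout (range 10% to 15%).

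SAP 3.5.1 lists the WPAI items, among them "Q2 = hours missed due to specified problem", and says that WPAI outcomes are percentages. It defines four scores, the first being "Percent work time missed due to problem", computed as Q2/(Q2+Q4). None of the four is in hours.

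The WPAI objective in SAP 2.2, and the matching analysis in Protocol 9.7.5, is "WPAI total lost productivity". For the analysis, SAP 5.4 says that "the Excel Table 6 summarizes the changes in percent overall work impairment and percent activity impairment at 12 and 24 weeks", each tested by paired t-test or Wilcoxon signed-rank test. The opening of SAP 5.4 and the association models in 5.5 refer to WPAI outcomes without listing them. SAP Section 6 titles Table 6 simply as change in WPAI.

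Enrolment is about 100 in SAP Section 4, about 55 in SAP 3.1 and 3.2, and about 52 in Protocol 9.5. Protocol 9.5 contains power statements for HAQ DI only.

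**The concern.** A power statement has meaning only for the variable and test to which its effect and SD belong. Here the inputs are in hours and the listed tests are on percentage scores. One of those scores mixes time off work with self-rated productivity at work, and the other has no working-hours term.

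Work productivity is part of the study's stated aim, and payers are a named audience. With the 80% left in place, a non-significant change in overall work impairment could be read as an adequately powered null. Nothing in the documents supports that reading.

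**Working it through.** **Inputs (SAP Section 4).** Mean improvement 9.9 hours; SD 25, reading ±25 as the SD of the change; two-sided alpha 0.05; power 0.80; dropout 13%; about half the patients working.

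**1. Reproducing 58.** For a paired mean change, by the normal approximation:

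n = [(1.960 + 0.842) × 25 / 9.9]² = 50.05

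With 13% dropout, 50.05 / 0.87 = 57.5, rounded up to 58. The plan's figure is reproduced as a dropout-inflated number of working patients. Without dropout, the normal approximation gives 51 and the noncentral t gives 53. A one-sided test gives 40 and a two-arm design 101 per arm, so neither of those was meant.

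**2. What 58 delivers for hours.** 58 × 0.87 = 50.5, or about 50 analysed pairs. The standardised effect is 9.9/25 = 0.396 and the noncentrality is 0.396 × √50 = 2.80. Paired t-test power is 78%.

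**3. Power for hours at the enrolment figures given.** Pairs = N × 0.5 × (1 − dropout), rounded down; power from the noncentral t with noncentrality 0.396 × √pairs.

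| Enrolled | Source | Pairs at 13% dropout | Noncentrality | Power | Power at 15% to 10% dropout |
|---|---|---|---|---|---|
| 100 | SAP Section 4 | 43 | 2.60 | 72% | 71% to 74% |
| 55 | SAP 3.1, 3.2 | 23 | 1.90 | 44% | 44% to 46% |
| 52 | Protocol 9.5 | 22 | 1.86 | 43% | 43% to 44% |

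Twice 58 is 116, not 100; 100 is twice the uninflated 50. That is why 100 enrolled falls below the target.

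**4. Whether the hours inputs carry over to the tested scores.** Write A = Q2/(Q2+Q4) for the fraction of work time missed. By the SAP's own formula, overall work impairment is A + (1 − A) × Q5/10. Its change depends on Q5, the rated effect on productivity while working, as well as on A. The documents give no mean or SD for a change in Q5 or in A. Activity impairment is Q6/10 and contains no hours. The inputs do not carry over, and the power of the two listed tests cannot be computed from the documents.

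**5. What can be said about the overall work impairment test.** At 55 enrolled, with half working and 10% to 15% dropout, 23 to 24 pairs remain. The change detectable with 80% power is then 0.60 to 0.61 SD. For an assumed SD of 20 to 35 percentage points (an assumption, since no SD is given), that is about 12 to 21 points.

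**The case against.** The strongest reply is that the paragraph is leftover text. Protocol 9.5 powers HAQ DI only, and the protocol's amendment log records that WPAI was removed as a factor in the sample size. On this view the hours calculation no longer governs anything, the WPAI objective is secondary and worded as description, and the larger problem is three different enrolment figures. Most of this stands. It settles the remedy, which is to delete the calculation rather than build new tests around it. It does not remove the fault, because SAP V0.4 still prints the calculation with its 80%.

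A reader might infer that absenteeism is never reported. The documents do not support that. Work time missed is a term in the overall impairment score that is tested, percent work time missed is a defined score, and the general references to WPAI outcomes in SAP 5.4 and 5.5 could include it. Table 6 has a broad title, and the table shells are a separate document that is not available here. What can be said is narrower: SAP 5.4 does not name percent work time missed as a separately summarised or tested change.

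A reader might also try to convert the hours into a share of the working week and so obtain a power figure for overall work impairment. The documents do not say what period the 9.9 hours cover, and they give nothing on the change in productivity while at work. If that also improved, power could be higher than the hours suggest. No such figure is defensible.

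Nor is 58 an arithmetic error; it reproduces.

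**Conclusion.** The point holds in this form: the 80% power in SAP Section 4 is for hours of work time lost, hours are not tested anywhere in the plan, and the power of the WPAI change tests that are listed is unknown.

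For hours themselves, the design gives about 78% power at 58 recruited working patients. It gives about 72%, 44% and 43% at total enrolments of 100, 55 and 52. These figures rest on reading ±25 as the SD of the change, on half the patients working, on 13% dropout that is the same in working and non-working patients, and on a paired t-test. Patients who change employment status or leave WPAI items blank would lower them.

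The fault is confined to a secondary endpoint and a power claim.

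**What to change.** Delete the work-time calculation from SAP Section 4, including the doubling to 100 that depends on it, so that the section matches Protocol 9.5. Add one sentence stating that no power is claimed for any WPAI endpoint. Keeping the hours figure with a caveat would leave the SAP at odds with the protocol. The remaining difference between 55 and 52 needs its own reconciliation.

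Optionally, add change from baseline at weeks 12 and 24 in percent work time missed, Q2/(Q2+Q4), to Table 6. It should be a descriptive row (n, mean, 95% CI) among employed patients, without a test. The items are already collected and the score is already defined. SAP V0.3 and V0.4 are both dated after the planned end of data collection (30 June 2018), so the row should be labelled as a late addition.

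The cost is a few lines of text and at most one table row. The SAP loses a favourable power statement and, if the row is added, gains one more unadjusted secondary summary on few pairs. No new patients or data are needed.

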## **5. STATISTICAL ANALYSIS**

### **5.1 General Considerations**

The statistical analysis will be performed using SAS® 9.3 software or a later version (SAS Institute, North Carolina, USA) via SAS Enterprise Guide version 6.1. The statistical results will be displayed using tables, listings and/or graphs. Figures will be performed with SAS®.

Unless otherwise specified, results will be provided as descriptive statistics. For categorical measures, data will include the frequency (number of cases [N]) and percentage (%) of total study patients observed in each category. Continuous variables

will be described with number of patients with missing observations, mean, standard deviation (SD), median, minimum, and maximum.

The following rules will be followed to define the number of decimal positions to report in study results:

- For categorical variables:
  - 1 for the percentage.
- For most of the continuous variables:
  - 1 for the mean, SD, median, minimum, and maximum.
  - In continuous variables with low values, 2 decimals for all measures will be reported.

A set of draft table shells (see the document, “Abbvie\_ROCKI\_Tableshell\_V0.3\_21Nov2018\_China.xlsx”) will be created in advance to describe the statistical analysis that will be done to fulfill the objectives of this study. Based on the analysis results the tables will be modified accordingly.

## 5.2 Analysis Plan for Demographic and Clinical Characteristics

- Descriptive statistics will be presented for patient demographics (Excel Table 1), and clinical characteristics (Excel Table 2) for all patients. The following measures will be assessed as of the patient’s baseline:
  - Patient age (mean, SD, minimum, maximum, median; categories: 18-34, 35-44, 45-54, 55-64, 65-74, 75+, missing)
  - Gender (male, female, missing)
  - Marital status (married, unmarried, missing)
  - Medical insurance type (National/Public insurance, Private insurance, Employer benefits, other, no insurance, missing)
  - Disease Activity Score in 28 joints - DAS28 (mean, SD, minimum, maximum, median; categories: Remission, Low Disease Activity, Moderate Disease Activity, High Disease Activity, Missing)
  - Number of patients with each of the comorbidities at baseline visit (See 3.5.2), and number of patients with any of these comorbidities

### 5.3 Analysis Plan for Primary Objectives

The objective of the primary endpoint analysis will be to demonstrate that treatment with adalimumab improves functioning as measured by the HAQ DI score in subjects with RA following treatment initiation (i.e. baseline).

- The changes in HAQ DI score at 12 and 24 weeks after the initiation of adalimumab will be presented (Excel Table 3.1); these changes will be summarized as the mean, SD, minimum, maximum, median, Q1, Q3; as well as the number and percent of patients achieving a clinically meaningful improvement on the HAQ DI, as defined by a -0.22 point improvement or greater. In addition, the mean or median change will be tested with a paired t-test or paired Wilcoxon signed-rank test without adjusting for baseline disease severity; for sensitivity analysis, the mean change will be analyzed using ANCOVA adjusting for baseline disease severity.
- The change in HAQ DI score at 24 weeks after the initiation of adalimumab (mean, SD, minimum, maximum, median, Q1, Q3), in those patients continuing on adalimumab (observed population) will be compared with those patients not continuing on adalimumab (withdrawal population). The mean or median changes in these two groups will be compared using an independent t-test or paired Wilcoxon signed-rank test listed in the table (Excel Table 3.2).

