9.7.3 Planned Methods of Statistical Analysis

All statistical tests will be two-tailed with a significance level of 0.05. Descriptive statistics will be provided. Descriptive analysis will be conducted on all key parameters and presented as mean, standard deviation, minimum, maximum, and median when continuous and as "n" and percent when categorical. Change from adalimumab initiation to 24 weeks will be calculated and evaluated for significant improvements using paired t-tests / ANOVA for parametric and Wilcoxon signed-rank for non-parametric data. Analysis will be also be conducted by severity level (moderate vs severe), disease duration quartile (to compare to prior work) and up to two (2) other subgroups. Cochran-Armitage test of trends or other similar methods may be used to compare categories of subjects.

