9.7.4 Primary Endpoint Analysis

The primary endpoint variable will be the change in HAQ DI score at week 24 after the initiation of adalimumab, in those patients continuing on adalimumab.

The objective of the primary endpoint analysis will be to demonstrate that treatment with adalimumab improves functioning as measured by the HAQ DI in subjects with RA following treatment initiation. This change will be summarized as the mean and 95% confidence interval and will be tested with a paired t-test.

The primary analysis will be summarized as the mean and 95% confidence interval and will be tested with a paired t-test without adjusting for baseline disease severity. For sensitivity analysis, the mean change in HAQ DI at week 24 will be analyzed using ANOVA adjusting for baseline disease severity.

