9.7.5 Secondary Endpoint Analysis

The main secondary endpoint variable will be the change in HAQ DI at week 12 after the initiation of adalimumab.

The objective of endpoint analysis will be to demonstrate that treatment with adalimumab improves functioning as measured by HAQ DI in subjects with RA compared to baseline.

The main secondary analysis will be summarized as the mean and 95% confidence interval and will be tested with a paired t-test without adjusting for baseline disease severity. For sensitivity analysis, the mean change in HAQ DI at week 12 will be analyzed using ANOVA adjusting for baseline disease severity.

Other secondary analysis include:

- Change in other patient reported outcomes (SF-36 domain scales, EQ-5D Index, WPAI total lost productivity) at weeks 12 and 24 after the initiation of adalimumab, in those patients continuing on adalimumab. These changes will be summarized as the means and 95% confidence intervals and will be tested with paired t-tests.
- Number and percent of patients achieving a clinically meaningful improvement on the HAQ DI, as defined by a -0.22 point improvement or greater, at weeks 12 and 24 after the initiation of adalimumab, in those patients continuing on adalimumab.

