**DOCUMENT HISTORY**

| Version # | Issue Date | Author/Editor | Sections Changed | Change Summary   |
|------------------|-------------------|----------------------|-------------------------|---|
| V0.4             | 30 May, 2019      | [REDACTED]           | Section 2, 5            | 
 
1. Add median (Q1, Q3) for describing continuous variables when normality is violated.
 
2. Use Q1, Q3 to replace 95% Confidence interval of mean, due to the violation of normality.
 
3. Added paired Wilcoxon signed-rank test as an alternative test for paired t-test when normality is violated.
 
  |
| V0.3             | 24 Dec, 2018      | [REDACTED]           | Section 2, 5            | 
 
1. Added paired Wilcoxon signed-rank test as an alternative test for HAQ DI and WPAI analyses, due to the violation of normality.
 
2. Changed ANOVA to ANCOVA for sensitivity analysis of HAQ DI change, because we used continuous DAS28.
 
3. Added Spearman correlation as an alternative method for association analyses, due to the violation of normality.
 
   |
| V0.2             | 2 Jan, 2018       | [REDACTED]           | Section 2, 5            | 
 
1. Patient's impression of change in RA at weeks 12 and 24 after the initiation of adalimumab has been added in the Study Objectives and Statistical Analysis Section according to protocol.
 
2. Disease status of RA (moderate, severe, missing) has been deleted in Table 2, since it's duplicated with DAS28 categorization.
 
3. Dosage of first adalimumab injection has been deleted in Table 2, since the DOSE should be 40MG for all adults.
 
 |
| V0.1             | 8 Aug, 2017       | [REDACTED]           | All                     | Initial Version   |

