### 2.1 Primary Objectives

- To describe the change in HAQ DI score at 24 weeks after the initiation of adalimumab (i.e. baseline), in those patients continuing on adalimumab (as observed population). This change will be summarized as the mean and 95% confidence interval or median (Q1,Q3) and will be tested with

a paired t-test or paired Wilcoxon signed-rank test without adjusting for baseline disease severity. For sensitivity analysis, the mean change in HAQ DI at Week 24 will be analyzed using ANCOVA adjusting for baseline disease severity.

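### SAP 5.3 and 5.4 omit the 95% confidence interval that the protocol requires for HAQ DI and other PRO changes and give quartiles instead; the fallback test for continuing versus not-continuing patients is a paired test on independent groups

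*SAP*

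**What the plan says.** **Protocol.** For the primary endpoint, section 9.7.4 says: "This change will be summarized as the mean and 95% confidence interval and will be tested with a paired t-test". Section 9.7.5 sets the same summary for the Week 12 HAQ DI change. For SF-36, EQ-5D and WPAI at both visits it says: "These changes will be summarized as the means and 95% confidence intervals and will be tested with paired t-tests". Section 9.7.3 allows a change of test when the data call for it ("paired t-tests / ANOVA for parametric and Wilcoxon signed-rank for non-parametric data") but does not withdraw the interval. For patients continuing versus not continuing adalimumab, section 9.7.6 names an independent t-test.

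**SAP.**
- Section 5.3, HAQ DI: "these changes will be summarized as the mean, SD, minimum, maximum, median, Q1, Q3; as well as the number and percent of patients".
- Section 5.4, SF-36, EQ-5D-3L and WPAI: "these changes will be summarized as the mean, SD, minimum, maximum, median, Q1, Q3; and the mean or median change". The list is the same in all three bullets.
- Section 2.1, HAQ DI at Week 24: "summarized as the mean and 95% confidence interval or median (Q1,Q3) and will be tested with" one of two tests. Section 2.2 words the Week 12 HAQ DI change in the same way and has "summarized as the means and 95% confidence intervals or median (Q1,Q3") for the other outcomes.
- The document history for V0.4 gives the intention: "Use Q1, Q3 to replace 95% Confidence interval of mean, due to the violation of normality".
- Sections 2.3 and 5.3 (Table 3.2) compare continuing with not-continuing patients by an independent t-test or, alternatively, a paired Wilcoxon signed-rank test.

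**The concern.** A single-arm before-after study reports, in effect, one number for its primary endpoint: the mean change. The 95% CI says how precisely that number is known. Quartiles answer a different question, namely how much individual patients differ. If they are printed where the interval used to be, a reader may take them for one and draw the wrong conclusion.

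Improvement against zero can still be judged, because the test, mean and SD remain. What is no longer firmly planned is any output that places the mean change, with its uncertainty, relative to -0.22, a threshold used in the power statement in Protocol 9.5. The responder percentage kept in SAP 5.3 counts patients who reach that cut-off and does not do this.

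The second part is a plain error of method. A signed-rank test needs one-to-one pairs. Under the note to Protocol 9.1, a patient is either continuing or not continuing, so there are none. The SAP history records normality as violated, so the fallback may well be used, and it is the only non-parametric test the SAP names for this comparison.

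**Working it through.** **Inputs (Protocol 9.5).** N = 52; 10% dropout; two-sided alpha 0.05. Scenario 1: mean change -0.21, SD 0.5. Scenario 2: mean change -0.5, SD 0.7, set against -0.22. Evaluable patients: 52 × 0.90 = 46.8, taken as 47.

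**The plan's own figure.** For scenario 1, a paired t-test (noncentral t) with 47 evaluable patients has 80.5% power, and 47/0.90 = 52.2. The planned 52 is reproduced to within rounding, so 47 is a fair basis.

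**Formulas.**
- 95% CI for the mean: mean ± t(0.975, n-1) × SD/√n, with t(0.975, 46) = 2.013.
- Quartiles of the individual changes, assuming a normal shape: mean ± 0.6745 × SD.

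**Results.**

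| Case | CI half-width | 95% CI | Quartile half-width | Q1 to Q3 |
|---|---|---|---|---|
| Scenario 1, n = 47 | 2.013 × 0.5/√47 = 0.147 | -0.36 to -0.06 | 0.6745 × 0.5 = 0.337 | -0.55 to +0.13 |
| Scenario 2, n = 47 | 2.013 × 0.7/√47 = 0.206 | -0.71 to -0.29 | 0.6745 × 0.7 = 0.472 | -0.97 to -0.03 |
| Scenario 2, n = 200 | 0.098 | -0.60 to -0.40 | 0.472 | -0.97 to -0.03 |

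In scenario 1 the CI excludes zero while the quartiles straddle it. In scenario 2 the CI lies wholly below -0.22 while the quartiles span it. Going from 47 to 200 patients roughly halves the CI and leaves the quartiles where they were.

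**Does non-normality justify dropping the interval?** Samples of n = 47 were simulated from a reflected, shifted gamma distribution with the planning means and SDs. Over 3,000 samples the t-based 95% CI covered the true mean 94.5% of the time at skewness -1 and 93.5% at skewness -1.5. A separate run of 40,000 samples gave 94.6% and 94.0%. Skew of that size costs about one percentage point of coverage or less in the larger run.

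**Group comparison.** With assumed group sizes of 47 and 5, the paired test stopped on unequal lengths and the rank-sum (Mann-Whitney) test ran. Had the sizes happened to match, the pairing would have been arbitrary.

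**The case against.** The strongest reply is that little is really lost. SAP 2.1 and 2.2 still name the interval as an option. SAP 5.3 and 5.4 keep the mean and SD, so with n reported anyone can rebuild a t-based CI. The table shells are not in the documents and, being dated before SAP V0.4, may still carry a CI column. All of this is true, and it limits the severity. It does not make the plan consistent, and a reader should not have to reconstruct the primary estimate's precision.

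Second, Protocol 9.7.4 plans no test of the mean against -0.22; in the analysis sections that figure is a patient-level cut-off. Scenario 2 is also a favourable case. Power against -0.22 at 47 patients is about 77% (difference 0.28, SD 0.7), not the 99% stated in Protocol 9.5, and in scenario 1 the CI itself spans -0.22. This stands as a caution: the interval will not always settle the question. It remains the planned output that would show whether it does.

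Third, the illustration assumes normality although the change was made because normality failed. HAQ DI is bounded at 0 and 3, floor effects were not modelled, and WPAI will have fewer observations because SAP section 4 expects about half the patients not to be working. A run at n = 23 gave coverage of 94.2%, 93.4% and 92.1% at skewness -1, -1.5 and -2. That is some loss with small n and strong skew. It may argue for a bootstrap or rank-based interval, but not for having none.

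Fourth, the faulty test is a second-named fallback for a comparison that the SAP calls exploratory and the protocol additional secondary, and one group may hold only about five patients (10% of 52). The practical weight is small, but the rule is still wrong as written.

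**Conclusion.** Both parts hold. SAP 5.3 and 5.4 omit an interval that Protocol 9.7.4 and 9.7.5 require, SAP 2.1 and 2.2 disagree with 5.3 and 5.4, and the stated reason does not support replacing a CI with quartiles. At the planning values the quartile range is about 2.3 times as wide as the CI (0.337/0.147 and 0.472/0.206) and does not shrink with sample size. These widths assume 47 evaluable patients and a normal shape; the coverage figures rest on the assumed gamma shape.

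The paired signed-rank test is acceptable for within-patient change and invalid for the two-group comparison. The primary test, the point estimate, the sample size and the first-named independent t-test are untouched. This should be fixed, but it does not threaten the primary conclusion about change from zero.

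**What to change.** 1. In SAP 2.1, 2.2, 5.3 and 5.4, state that the mean change with its 95% CI is always reported at Weeks 12 and 24, whichever test is used. Keep Q1 and Q3 as description only.
2. Where the signed-rank test is used for within-patient change, add an interval that matches it, such as the Hodges-Lehmann estimate with 95% CI. Neither document names this estimator. It is one suitable choice, and it accompanies the CI for the mean rather than replacing it.
3. In SAP 2.3 and 5.3 (Table 3.2), replace the paired Wilcoxon signed-rank test with the Wilcoxon rank-sum (Mann-Whitney) test.
4. While editing Table 4, note that SAP 5.4 tabulates the SF-36 physical and mental component scores, whereas Protocol 9.7.5 asks for the domain scales. A CI column alone would not deliver the protocol's output there.

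The cost is SAP wording and a CI column in Tables 3.1 and 4 to 6, if the shells do not already have one. No new data are needed, and sample size, power and alpha do not change.

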6.0 Milestones

Major study milestones and their planned dates are as follows:

Start of Data Collection (FPFV):	15 April 2016
End of Data Collection:	30 June 2018
Study Progress Report:	Not Applicable
Registration in the EU PAS register:	Not Applicable
Final Report of Study Results:	31 December 2018

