9.5 Study Size

Approximately 52 patients diagnosed with RA will be recruited. The planned sample size provides 80% power for detecting a statistically significant improvement in HAQ-DI (Δ HAQ-DI < 0) assuming a mean Δ HAQ-DI of -0.21 and a standard deviation of 0.5 (reference 11), at two-sided significance level of 0.05 and accounting for a 10% dropout rate. The sample size also provides 99% power for detecting a statistically significant clinically meaningful improvement in HAQ-DI (Δ HAQ-DI < -0.22) assuming a mean Δ HAQ-DI of -0.5 and a standard deviation of 0.7, at two-sided significance level of 0.05 and accounting for a 10% dropout rate.

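### The SAP leaves the primary HAQ DI test open between a paired t-test and a signed-rank test, with no decision rule, where protocol 9.7.4 names only the t-test on the mean

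*SAP*

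**What the plan says.** Protocol 9.7.4 is specific about the primary endpoint: "The primary analysis will be summarized as the mean and 95% confidence interval and will be tested with a paired t-test", with no adjustment for baseline severity. Protocol 9.5 sizes the study on the same quantity: "The planned sample size provides 80% power for detecting a statistically significant improvement in HAQ-DI", for a mean change of minus "0.21 and a standard deviation of 0.5".

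Protocol 9.7.3, the general methods section, assigns t-tests to parametric data and the signed-rank test to non-parametric data when change to 24 weeks is evaluated. It does not say how the data are to be classified.

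SAP 5.3 states for HAQ DI that "the mean or median change will be tested with a paired t-test or paired Wilcoxon signed-rank test". SAP 2.1 offers the same alternatives, with either the mean and its 95% CI or the median and quartiles as the summary. SAP 5.3 lists mean, SD, range, median and quartiles, but no confidence interval.

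The SAP document history explains the alternative. V0.3 (24 December 2018): "Added paired Wilcoxon signed-rank test as an alternative test for HAQ DI and WPAI analyses, due to the violation of normality". V0.4 (30 May 2019) extends it to paired t-tests generally and substitutes the quartiles for the CI of the mean, again citing non-normality. In protocol 6.0 the milestone "End of Data Collection" is planned for 30 June 2018.

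**The concern.** A primary analysis should be one test of one hypothesis, fixed without reference to the results. Here two tests are allowed, nothing in the analysis text says which applies, and the history suggests that the second was added because the HAQ DI data had been seen to be non-normal.

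The tests are not interchangeable. The t-test concerns the mean change, on which the study was sized. The signed-rank test concerns the pseudo-median, which equals the mean when changes are symmetric but not, in general, when they are skewed. Skewness is one of the departures that would trigger a switch, so the hypothesis could change just when the difference matters.

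Two consequences follow. The primary p-value could be challenged as chosen after the data were seen. And the effect could be reported with quartiles, which describe spread between patients, in place of an interval for the precision of the mean. The SAP's ANCOVA sensitivity analysis still models mean change, so after a switch it would no longer check the quantity that the primary test addresses.

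**Working it through.** **Inputs.** Protocol 9.7.3: "All statistical tests will be two-tailed with a significance level of 0.05". Protocol 9.5: mean change -0.21, SD 0.5, 80% power, "accounting for a 10% dropout rate", about 52 patients recruited. The documents give no normality test and no distribution for the changes, so both are assumed below.

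**1. Reproduce the plan's figure.** For a paired t-test the noncentrality is √n × 0.21/0.5 = 0.42√n, with n - 1 degrees of freedom.
- n = 46: power 79.6%. n = 47: power 80.5%. So 47 evaluable patients are needed.
- 47/0.9 = 52.2, and 52 × 0.9 = 46.8.

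The stated 52 is therefore a t-test calculation on the mean, to within one patient. If the signed-rank test were primary and changes were normal, power at 47 would be about 78.5%, and the need would be 47 × π/3 = 49.2, so about 50 evaluable (50/0.9 = 55.6, or 56 recruited).

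**2. Why the hypotheses differ.** Take an exponential shape (skewness 2) with mean 0, SD 0.5 and the long tail toward worsening. The sum of two unit exponentials has median 1.678, so the pseudo-median of the change is 0.5 × (1.678/2 - 1) = -0.08. The mean is zero, yet the signed-rank test sees an improvement.

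**3. Simulated error rates.** n = 47, SD 0.5, true mean change 0. Assumed rule: Shapiro-Wilk p < 0.05 leads to the signed-rank test, otherwise the t-test. Centred gamma changes, 6,000 to 8,000 replicates.

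| Skewness | t-test, two-sided | Gated rule, two-sided | Gated rule, false improvement, tail toward worsening | Gated rule, false improvement, tail toward improvement |
|---|---|---|---|---|
| 0.7 | 5.3% | 7.0% | 5.6% | 1.5% |
| 1.0 | 5.5% | 9.1% | 7.8% | 1.0% |
| 1.4 | 6.1% | 14.0% | 12.8% | 0.3% |
| 2.0 | 6.4% | 21.3% | 20.5% | 0.1% |

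The directional columns come from separate runs. Because the two tails are mirror images, they should add up to the two-sided rate: at skewness 1, 7.8% + 1.0% = 8.8%, against 9.1%. The Monte Carlo standard error there is about √(0.09 × 0.91/6000) = 0.4 points. Another set of runs gave 7.1%, 9.8%, 13.9% and 21.6% for the gated rule. A 20,000-replicate run gave 9.0% and 21.5% at skewness 1 and 2, with the t-test at 5.6% and 6.6%.

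Symmetric changes (20,000 replicates):

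| Shape | t-test | Gated rule | Smaller of the two p-values |
|---|---|---|---|
| Normal | 5.1% | 5.1% | 5.9% |
| Laplace | 4.7% | 5.0% | 6.3% |
| t, 3 df | 4.7% | 5.3% | 6.6% |

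**4. Power at a mean of -0.21, tail toward improvement.** At skewness 1 the t-test has 84% and the gated rule 70%. At skewness 2 the figures are 88% and 56%.

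**5. Timing.** V0.3 is dated just under six months after the planned end of data collection, and V0.4 eleven months after it. The V0.3 entry also explains the move to ANCOVA in the past tense, by the use already made of continuous DAS28. This suggests that analyses had been run.

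**The case against.** The strongest reply is that the protocol had already provided for this. Section 9.7.3 names the signed-rank test for non-parametric change to 24 weeks, which is the primary time point, and section 9.7.1 presents the protocol's analysis text as an overview to be detailed in the SAP. This stands in part. A reader might infer that the SAP introduced a wholly new test after the fact, and the documents do not support that. But 9.7.3 gives no criterion, and 9.7.4, the specific provision, names only the t-test.

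A reader might also infer that the analyst may take whichever p-value is smaller. The V0.4 history entry ties the alternative to violated normality, so that is not the stated intention. What is missing is how a violation is judged.

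Nor do the documents support a blanket claim of inflated false-positive risk. If nothing changes between visits in the sense that the two scores are exchangeable, differences are symmetric and the signed-rank test holds its level. If skewness runs toward large improvers, the switch is conservative for claims of improvement. With heavy but symmetric tails the signed-rank test is the more powerful (96% against 84% for t with 3 df). At the protocol's other scenario (mean -0.5, SD 0.7), both approaches rejected in at least 97.8% of runs in the skewed cases examined.

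Finally, mean-based results do not vanish. SAP 5.3 keeps the mean and SD, from which a CI can be computed, and SAP 2.1 keeps the CI as an option. That limits the loss but does not settle which result is primary.

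**Conclusion.** The point holds as a mismatch and a missing rule. The protocol fixes the primary test and estimate in 9.7.4, the SAP leaves both open, and the stated reason for the alternative is a property of the data.

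That the choice was data-driven is an inference, though a fair one. A reader might take it as established that collection had ended when the alternative was added, but 30 June 2018 is a planned date and the actual date is not given.

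The numerical effect is conditional on the assumed gate and gamma shapes at n = 47. Two-sided error for the hypothesis of zero mean change is about 7% to 22% at skewness 0.7 to 2.0, against 5% to 7% for the t-test. False improvement is about 6% to 21% if the tail is toward worsening and about 1.4% to 0.1% if it is toward improvement, where the cost is lost power. With symmetric changes the error is near 5%. The documents give neither the direction nor the size of any skewness, so none of these figures is a prediction for this study.

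A reader might also treat the -0.22 criterion as further evidence that everything rests on the mean. As an endpoint it is a per-patient response cut-off; only the second power statement in protocol 9.5 applies it to a mean.

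**What to change.** - In SAP 2.1 and 5.3, make the paired t-test, with the mean change and its 95% CI, the single primary analysis of HAQ DI at week 24, whatever a normality check shows. List the CI explicitly in 5.3.
- If changes are skewed, add a bootstrap CI for the mean as a sensitivity analysis. The t-test itself drifts to about 6% to 7% at skewness 1.4 to 2.0, so this is worth having.
- Report the signed-rank test and the median with quartiles as supportive, and state when and why they were added.
- Reconcile protocol 9.7.3 with 9.7.4, so that the general sentence does not appear to govern the primary endpoint.

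Stating a normality criterion and reporting both tests would remove the ambiguity, but the primary hypothesis would still depend on the data. Fixing the t-test keeps test, estimate and sample size on one quantity and leaves 52 patients unchanged. The cost is wording, one interval in the primary table and, if used, a short bootstrap program.
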